The study will prospectively enroll patients seen at the Pediatric IBD center of the Goryeb Children's Hospital. All pediatric patients diagnosed with IBD will be offered enrollment in the study. Data collection surveys will be initially completed at the time of consent (time 0), start of the yoga (time 1) session, end of the yoga session (time 2) and three months after completion (time 3) to determine if the effects of yoga are lasting. Each patient will serve as their own control with the difference between time of enrollment (time 0)/start of yoga (time 1) and start of yoga (time 1)/end of yoga (end of 2) being compared. Patients will enroll in a twelve class series offered twice a year. The classes will be open to a maximum of ten students and will continue to be offered once a week with encouragement to practice daily at home. Patients will have the option to attend a fall or spring set of classes to increase flexibility and improve enrollment.

Through the entire study period patients will receive standard medical therapy as determined by their specific pediatric gastroenterologist. Clearance by their primary gastroenterologist will be required in the 8 week time period prior to starting yoga to confirm they are healthy enough to start yoga.

Sample Size: Based on what has been determined to be the minimal clinically significant difference¹⁴ of HRQOL using the pedQL survey, we would need 34 patients in total as each patient will serve as their own control. . With a sample size of 34 patients, there will be 80% power to detect a 10-point increase (improvement) in average total PedsQL score (0-100 scale)]. The sample size calculation was based on standard deviation of the total score in the Control group = 15.4, probability of Type I error (alpha) of 0.05, and probability of Type II error (beta) of 0.20. That is, in only 20% of the times we will fail to reject the null hypothesis when it is in fact false; i.e. there is a difference.

Recruitment will be feasible over a two-year study time frame as we care for over 800 active IBD patients in our center.

Inclusion Criteria:

- Both male and female patients with IBD.
- Age 10-17 years
- Not currently practicing specific mind-body techniques (yoga, pranayama, biofeedback, hypnosis, guided imagery)
- Diagnosis of IBD

Exclusion Criteria: Other Chronic systemic disease ex. RA, CF, Celiac. Any chronic neurologic condition.

Yoga Introduction:

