Yoga is one component of Ayurveda, which is the complete traditional system of healthcare practiced in India and Sri Lanka. Understanding an individual's constitution and energy is a key part of Ayurvedic medicine. Each person's constitution is felt to be a balance of three types of energy, also known as the doshas. In Ayurveda, inflammatory disorders of the gut are primarily due to an imbalance of 'pitta' dosha of the Anna Vaha Srotas (Digestive System). Anna vaha srotas has the important functions of digestion, absorption, and assimilation. Anna vaha srotas and respiration have integrated functioning according to Ayurveda. If one breathes deeply, it increases the secretion of digestive enzymes. People who do pranayama (deep breathing regularly, in general tend to have a strong appetite, because pranayama stimulates anna vaha srotas agni (digestive fire).

Pitta pacifying poses include forward bends and twisting yoga poses stimulate the digestive system. Forward bends are calming and reduce stress. Inversions stimulate the endocrine system. All of these effects are felt to be beneficial for a healthy digestive system.

Our yoga program will consist of a 12 week program, one class session per participant, per week. Classes will be offered once a week at Goryeb Children's Hospital/Atlantic Health System, Morristown, NJ. Classes will be one hour in duration. We will offer two sessions a year.

The yoga teacher will be certified in Hatha yoga, which is the most common form in America, and be registered with the Yoga Alliance. We will require a minimum of 500 training hours.

Yoga Class description:

WARM UP/COOL DOWN:

- Breathing Techniques, Relaxation-Guided Imagery, Progressive Muscle Relaxation
- Yoga poses - see appendix 1

- Contraindications: Glaucoma, neck injury
- Poses will be modified to adjust for these contraindications

MODIFICATIONS TO ROUTINE:

Certain symptoms dictate modification of some of the yoga poses. All patients will be advised at the start of class to inform the teacher if they are menstruating, have nausea/vomiting, are dizzy, or are experiencing severe pain/flare/active bleeding. Patients will also be reminded to let the teacher know if they have a cold/cough/bronchitis/asthma exacerbation on the day of class, or if they have had a recent neck/back injury. They may be instructed not to participate in class at all that day, or to refrain from participating in certain asanas/poses that day.

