We will record what medications the patient is currently using, including steroids, biologics and immune modulators. The dose of medications will also be recorded in order to determine such information as the total dose of steroids, per patient over the study period.

- Yoga Questionnaire:

The yoga questionnaire will consist of questions about past exercise experience, use of other non-mind/body CAM such as probiotics, herbs and supplements. Post yoga the questionnaire will consist of questions if they plan to continue to practice after the study is complete.

- Follow up questionnaire:

Questionnaire will be sent for those subjects who have completed at least nine classes. The follow up questionnaire consists of 5 questions to evaluate if they are still practicing yoga, any benefit from being in the yoga study, has it helped manage their IBD and would they participate in a follow up yoga study.

In addition to the questionnaire/outcome measure collected at baseline and at the different endpoints (Impact III, peds QL, self efficacy scale, PCDAI, PUCAI), baseline demographic and clinical data will be gathered for each patient in the study. Those include age, gender, race, disease type (crohn's, UC), date of diagnosis, areas of bowel involved, medications and dose of steroids.

V. Planned Data Analysis:

Baseline demographic data will be collected and descriptive statistics will be used to profile the patient population. Clinical factors collected at baseline and post intervention and the differences will be

analyzed between the yoga and control group. Categorical data will be analyzed using chi-square or Fisher's exact tests. The distribution of all continuous data will be examined. For continuous variables whose distributions approximate normality, a t-test will be used for comparisons. When normality assumptions are not satisfied, the non-parametric Mann-Whitney U test will be utilized.

The data from the questionnaires will be collected via REDCap secure access.

Statistical significance is considered at $p < 0.05$. All statistical analyses will be performed using MINITAB 17.

VI. Benefits and Risks:

We anticipate the participants who complete the yoga program will have improved HRQOL and self-efficacy. All participants may experience a personal satisfaction by their contribution to a clinical investigation.

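### Yoga is taught in about four class series, but the power figure and planned tests assume independent patients; if changes correlate within a series, precision is overstated by an unknown amount

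*Combined protocol and SAP*

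**What the plan says.** Section IV (Participants and Enrollment) describes weekly live classes over twelve weeks, taken as a fall or spring series: "The classes will be open to a maximum of ten students". The class description later in that section adds "We will offer two sessions a year". Recruitment is expected to take two years.

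Each patient is their own control. The change from enrollment (time 0) to the start of yoga (time 1) is compared with the change from the start to the end of yoga (time 2).

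Under Sample Size, "we would need 34 patients in total as each patient will serve as their own control", and "With a sample size of 34 patients, there will be 80% power to detect a 10-point increase (improvement) in average total PedsQL score". The inputs are "standard deviation of the total score in the Control group = 15.4" and "probability of Type I error (alpha) of 0.05". No ICC, design effect, number of series or SD of change is given.

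Section V says: "For continuous variables whose distributions approximate normality, a t-test will be used for comparisons". Mann-Whitney U is the fallback. It words the comparison as one between a yoga group and a control group, although there is a single group. It has no term for class.

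**The concern.** Patients in one series share peers, class dynamics and calendar dates. The PedsQL covers social, school and emotional functioning, which a peer group or the school calendar could affect.

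Taking differences within a patient removes stable differences between series. It does not remove a shared effect that arises only between time 1 and time 2, because the waiting period from time 0 to time 1 contains no class to offset it. Such an effect makes the contrasts of classmates positively correlated.

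A test that counts 34 independent patients would then use too small a standard error. The trial could report a benefit with more confidence than about four series can support.

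**Working it through.** **Inputs from the plan:** n = 34, difference 10 points, SD 15.4, alpha 0.05 (sidedness not stated; two-sided used here), power 80%, class maximum ten, two series a year, two years. **Assumed, not in the documents:** series of 9, 9, 8 and 8; no dropout; ICC of the within-patient contrast 0.02, 0.05 and 0.10.

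1. **Number of series.** 2 per year × 2 years = 4. The cap gives the same minimum: 34/10 = 3.4, so at least 4. Average size is 34/4 = 8.5.

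2. **The plan's own figure.** n = (SD × (1.960 + 0.842)/10)².
   - If 15.4 is the SD of the within-patient quantity: (15.4 × 2.802/10)² = 18.6, so 19 patients (21 by the t distribution). Power at 34 is about 96%.
   - For two uncorrelated measurements: SD = 15.4 × √2 = 21.78, n = 38 (40 by t). Power at 34 is 76% (74% by t).
   - One-sided, the same two cases give 15 and 30 (17 and 31 by t).
   - The Section IV contrast is (T2 − T1) − (T1 − T0) = T2 − 2·T1 + T0. With equal variances and a common correlation r, its SD is 15.4 × √(6(1 − r)). At r = 0.5 this is 26.67 and n = 56; at r = 0.7 it is 20.66 and n = 34. It equals 15.4 only at r = 1 − 1/6 = 0.83.

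   So 34 at 80% appears only with an unstated assumption. Taking the 80% at face value for a paired t-test implies a contrast SD of 20.2.

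3. **Effect of series.** Design effect DE = 1 + (m* − 1) × ICC, with m* = Σm²/n = (81 + 81 + 64 + 64)/34 = 290/34 = 8.53. Effective n = 34/DE. Type I error is simulated for a one-sample t-test on the 34 contrasts (at least 40,000 null trials per ICC). Power is by noncentral t at the effective n.

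| ICC | DE | Effective n | Type I error | Power, SD 20.2 | Power, SD 15.4 |
|---|---|---|---|---|---|
| 0 | 1.00 | 34.0 | 5.0% | 80% | 96% |
| 0.02 | 1.15 | 29.6 | about 6.5% | 74% | 93% |
| 0.05 | 1.38 | 24.7 | about 9.5% | 66% | 87% |
| 0.10 | 1.75 | 19.4 | about 14% | 54% | 77% |

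   The type I error column does not depend on the SD. The power columns do.

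4. **Analysis on series means.** Four series leave 3 degrees of freedom (df). At ICC 0 the noncentrality is 10 × √34/20.2 = 2.89, giving power 50.5%; with SD 15.4 it is 10 × √34/15.4 = 3.79, giving 71%.

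5. **If Section V's two-group wording is followed literally.** These are simulated type I errors of an unpaired t-test.
   - Time 1 against time 2 scores, correlation 0.5: 0.7%, 2.0% and 3.8% at ICC 0, 0.05 and 0.10. With correlation 0.1: 4.0%, 7.9% and 12.0%.
   - The two changes treated as independent groups: about 11%, 17% and 22%. They share time 1 with opposite sign, so the test is too liberal even without clustering.

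**The case against.** A reader might infer that the true power is below 80% and that the trial's p-values are too small without qualification. The documents do not support that stronger reading, for three reasons.

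- **No ICC is given.** Only correlation in the change matters, and it could be small. Section IV refers to one yoga teacher; if the same person leads every series, the teacher adds no variation between series.
- **The 80% is not a firm base.** If 15.4 were the SD of the contrast, power would stay above 80% at ICC 0.02 and 0.05 and fall below it only at 0.10. Against this, the plan describes 15.4 as the SD of the score, and the contrast has that SD only if the correlation is about 0.83. The missing SD is the more basic gap.
- **The direction of error depends on the test.** Section V can be read as an unpaired comparison, which may be conservative on scores or liberal on changes, whatever the class effect.

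A class-level primary analysis would also be costly. Beyond the loss of power on 3 df, the estimated series variance would be zero or negative in about 52%, 44% and 33% of trials at ICC 0.02, 0.05 and 0.10, so a random effect is barely estimable.

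These points limit the claim and the remedy. They do not supply the missing allowance for class: for a paired test on the Section IV contrast, any positive ICC pushes the error rate above 5%.

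**Conclusion.** The concern holds conditionally. About four series supply the 34 patients, and neither the sample size nor Section V allows for this. If the within-patient contrast correlates within series, a paired t-test exceeds its nominal 5% (about 6.5%, 9.5% and 14% at assumed ICCs of 0.02, 0.05 and 0.10) and effective sample size falls to about 30, 25 and 19. These figures rest on the assumed ICCs, series of 9, 9, 8 and 8, and no dropout. Whether true power is above or below 80% cannot be settled from the documents. The omission limits how firmly a benefit can be claimed; it does not invalidate the design.

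**What to change.** 1. **Section V.** Name the within-patient PedsQL contrast (time 1 to 2 change minus time 0 to 1 change) as the primary analysis, with a paired test, in place of the two-group wording. Report the mean contrast for each class series. Add a sensitivity analysis that accounts for series: either series means on about 3 df or a random series effect with a small-sample df correction. State that the conclusion will be qualified if the two analyses disagree.

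2. **Sample Size.** First state the SD of that contrast and its source. Then say that the power assumes no class effect, and show power over ICC 0.02 to 0.10, labelled as an assumption.

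The cost is some rewording and one extra analysis. Series membership is known from enrollment, so no new patients or measurements are needed. The plan should admit the downside: the class-level interval will be wide, and that analysis has only about 51% power at ICC 0 if the contrast SD is 20.2, or about 71% if it is 15.4. A non-significant sensitivity result is therefore weak evidence against a benefit, and it should be read through its estimate and interval.

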Patients will each serve as their own control and complete questionnaires at enrollment and at the start and end of the 12-week group yoga class sessions. They will also complete the questionnaires three months after finishing the class sessions. . The program will consist of a live group class session over 12 weeks. Baseline and follow-up questionnaires will be used to determine there are changes in QOL, self-efficacy, and disease response.

I. Specific Aims:

1. Primary Aim: To determine if a structured Yoga program, in addition to standard medical therapy, improves health related quality of life (HRQOL) in pediatric patients diagnosed with IBD

2. Secondary Aim:

To determine if, in pediatric patients recently diagnosed with IBD, a structured Yoga program:

- Improves self-efficacy

II. Background and Significance:

Approximately 25% of Inflammatory bowel disease (IBD) is diagnosed in the pediatric age group with the peak age of onset in the adolescent years¹. Adolescence is a time of great psychosocial growth. IBD adds additional stressors of a chronic disease with unpredictable and potentially embarrassing symptoms. Side effects of steroid treatment, such as acne, weight gain, and mood changes, as well as delayed puberty, may further ostracize youth with IBD. The incidence of psychiatric disorders, is increased compared to healthy children and is comparable to other chronic diseases such as cystic fibrosis². HRQOL may be impaired by issues of pain, school absences, and concerns about the chronic nature of IBD and patients with increased disease severity often have worse HRQOL².

Various strategies have been tried to improve HRQOL and psychosocial functioning in pediatric IBD patients. A prospective analysis of HRQOL and anxiety in children attending a one week camp sponsored by the Crohn's and Colitis foundation of America demonstrated improvement in the quality of life³. A cognitive behavioral therapy (CBT) program, which included relaxation training and pain-coping strategies, increased a feeling of control and decreased helplessness in adolescents⁴. More recently a skills based psychological intervention program, which included relaxation, imagery and deep-breathing as part overall CBT program, showed significant reductions in somatization symptoms in a group of adolescent girls with IBD and their parents when pre and post-treatment variables were compared⁵.

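### The 80% power claimed for 34 patients does not follow from the stated inputs; the SD of the within-patient contrast, or a between-visit correlation, is missing

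*Combined protocol and SAP*

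**What the plan says.** Section IV, Sample Size, derives the size from a difference held to be clinically meaningful on the PedsQL and concludes "we would need 34 patients in total as each patient will serve as their own control". It then claims "With a sample size of 34 patients, there will be 80% power to detect a 10-point increase (improvement) in average total PedsQL score". The variability input is given as follows: "The sample size calculation was based on standard deviation of the total score in the Control group = 15.4". Alpha is 0.05 and beta 0.20. Sidedness, an SD of change, a between-visit correlation and a dropout allowance are not stated.

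The comparison is described in three places:

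- Lay Summary: "Patients will each serve as their own control".
- Section IV, Participants and Enrollment: "Each patient will serve as their own control with the difference between time of enrollment (time 0)/start of yoga (time 1)" set against the difference from time 1 to time 2, the end of yoga. This compares two consecutive changes within the same patient.
- Section V, Planned Data Analysis: differences in clinical factors are "analyzed between the yoga and control group". Continuous variables get a t-test, not described as paired, and where normality fails "the non-parametric Mann-Whitney U test will be utilized".

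**The concern.** In an own-control design, precision is set by the SD of the quantity computed within each patient. The SD of scores across patients at one visit does not determine it. The only SD given is of the second kind, and it is attributed to a control group that the design does not have. A correlation between visits, or the SD of the contrast itself, is needed to get from 15.4 to a power figure.

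The contrast is not settled either. The power sentence speaks of a "10-point increase (improvement) in average total PedsQL score", which reads like a simple change. The enrollment text compares two changes, which is a noisier quantity. Section V refers to two groups.

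This paragraph is the only basis given for enrolling 34 patients and it concerns the primary aim. If the true power is well below 80%, a null result says little about a 10-point effect. If it is well above, the trial is larger than its own criterion requires. A reader cannot tell which applies.

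**Working it through.** **Inputs from section IV:** n = 34; difference 10 points; SD of the total score 15.4; alpha 0.05; target power 80%. Sidedness is not stated, so both versions are shown. Power is from the non-central t distribution.

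**Step 1. Try to reproduce 80% at n = 34 from the stated inputs alone.** Standardised difference: 10/15.4 = 0.649.

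| Reading | n for 80% (two-sided / one-sided) | Power (two-sided / one-sided) |
|---|---|---|
| 15.4 is the SD of the paired difference, n = 34 | 21 / 17 | 95.7% / 98.0% |
| Pre-post change, zero correlation, SD = 15.4 × √2 = 21.8, n = 34 | 40 / 31 | 74% / 84% |
| Two groups, 17 each | 39 / 31 per group | 45% / 58% |
| Two groups, 34 each | 39 / 31 per group | 75% / 84% |

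None gives 80%. The two-group rows only rule out readings; they are not estimates of this trial's power.

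**Step 2. What SD would make the claim true?** Solving for 80% power at n = 34 and a 10-point difference gives a contrast SD of 20.2 (two-sided) or 23.0 (one-sided). Neither value is in the document.

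**Step 3. Power for the contrast in the enrollment text.** With Y0, Y1 and Y2 the scores at times 0, 1 and 2, the contrast is (Y2 − Y1) − (Y1 − Y0) = Y2 − 2Y1 + Y0. Assume SD 15.4 at each visit.

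- Equal correlation r between all visits: SD = 15.4 × √(6(1 − r)).
- Decaying correlation (r for adjacent visits, r² for times 0 and 2): SD = 15.4 × √(6 − 8r + 2r²).

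The protocol gives no correlation, so every r below is an assumption.

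| r | SD, equal | Power two-sided / one-sided, equal | Detectable difference at 80%, two-sided, equal | Power two-sided / one-sided, decaying |
|---|---|---|---|---|
| 0.5 | 26.7 | 56% / 69% | 13.2 | 64% / 76% |
| 0.6 | 23.9 | 66% / 77% | 11.8 | 76% / 85% |
| 0.7 | 20.7 | 78% / 87% | 10.2 | 88% / 93% |
| 0.8 | 16.9 | 92% / 96% | 8.4 | 97% / 99% |

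Power reaches 80% at r of about 0.71 (two-sided) or 0.63 (one-sided) with equal correlation, and at about 0.64 or 0.55 with decaying correlation.

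**Step 4. Power for the simple time 1 to time 2 change.** SD = 15.4 × √(2(1 − r)). Two-sided power is 74% at r = 0, 80% at r = 0.14 and 96% at r = 0.5.

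At the same r = 0.5, the choice of contrast alone moves two-sided power from 56% to 96%.

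**Step 5. Could an unreported input give 34?** Yes. For the change-versus-change contrast at r = 0.70, 6(1 − r) = 1.8, and the normal formula gives (1.960 + 0.842)² × 15.4² × 1.8 / 10² = 33.5, which rounds up to 34.

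**The case against.** The strongest reply is that nothing has been shown to be miscalculated. Step 5 shows that an unreported correlation near 0.7 would give 34, so the fault may be an omitted input and not a wrong figure. There are other routes to 34. A one-sided normal-formula n of 30 inflated for 10% dropout is 30/0.9 = 33.3, or 34. Doubling the one-sided paired n of 17 also gives 34. The sentence on an increase is directional, so a one-sided origin cannot be excluded. On the simple-change reading, 34 patients give at least 80% for any r of about 0.14 or more. Finally, the group comparison in section V refers to clinical factors and does not name the PedsQL.

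Much of this is fair. It is not shown that 34 is too few, and the sponsor may hold a valid calculation. But each route needs a step the protocol does not report. Doubling is invalid when each patient is their own control, and the dropout route does not fit a sentence that attaches the 80% to the 34 patients themselves. That several incompatible routes end at 34 shows the text does not identify the calculation. On section V, no paired test is named for any outcome, and the Mann-Whitney test is for independent samples, so that section does not settle the contrast.

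**Conclusion.** The concern holds. From the stated inputs, 80% power at n = 34 cannot be reproduced: the readings give 95.7%, 74%, 45% or 75% two-sided, and 98%, 84%, 58% or 84% one-sided. The SD that would support the claim, 20.2 or 23.0, is not stated, and neither is a correlation that would lead to it.

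The direction of the discrepancy is unknown. For the change-versus-change contrast, two-sided power is below 80% unless the correlation is at least about 0.71 (equal) or 0.64 (decaying). For a simple change it is below 80% only if the correlation is under about 0.14. These figures assume SD 15.4 at every visit, all 34 patients analysed, and correlations chosen here to show the range. The finding that the stated inputs do not give 80% does not depend on those correlations. Because this is the sole justification of the sample size for the primary aim, it must be corrected.

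**What to change.** Keep 34 patients and make four changes.

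1. Name one primary PedsQL contrast in section IV. The enrollment text describes (time 2 − time 1) − (time 1 − time 0). If the simple time 1 to time 2 change is meant, say so in both places.
2. In section V, specify the matching paired analysis: a paired t-test, or the Wilcoxon signed-rank test if normality fails. Reconcile the yoga-versus-control wording and the Mann-Whitney test with it.
3. In the Sample Size paragraph, state the sidedness, say that 15.4 is a cross-sectional SD and where it comes from, and give the sponsor's own assumed between-visit correlation or contrast SD with its source.
4. Replace the unsupported 80% with the power or detectable difference that those inputs give, shown over a range of correlations. If the documented inputs give 80%, the figure stands with its derivation.

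The cost is one rewritten paragraph in section IV and one sentence in section V, with no extra patients. The stated power may turn out less favourable.

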The teacher will present modifications to the routine (such as avoiding inverted poses) for patients who are menstruating or having an active flare of GI symptoms.

Data collection measures :

- Impact III:

This is a validated, disease-specific pediatric questionnaire that measures HRQOL in pediatric IBD¹⁶ patients age 9-17 years. It consists of 35 questions and six domains: IBD symptoms, systemic symptoms, emotional functioning, social functioning, body image, and treatment/interventions. The answers are scored on a 5 point Likert response scale.

- Peds QL:

This is a validated pediatric questionnaire that measures general HRQOL in children ages 8-17 years¹⁴. It consists of 23 questions in areas of social, school, emotional and physical functioning. The answers are scored on a 5 point scale and then reverse scored and linearly transformed to a 0-100 scale.

- General Self-Efficacy Scale:

This is a widely used simple 10 item scale that measures a patient's a general sense of perceived self-efficacy, aiming to predict coping with daily life as well as adaptation after stressful life events¹⁷. It is a measure that has been validated in adolescents age 12 and above.

- PCDAI and PUCAI :

The Pediatric Crohn Disease Activity Index (PCDAI) and Pediatric Ulcerative Colitis Activity Index (PUCAI) are validated disease activity indices that include patient symptoms in the previous seven days, physical exam findings, growth parameters

and laboratory studies¹⁸. The information needed to complete this index will be available through the patient's chart as the data collected is part of routine care.

- Physician Global Assessment :

This is a global assessment is part of routine care and determined by the patient's primary GI doctor. The assessment is a global measure of disease activity with the following five categories: inactive, mild, moderate, severe, NA/unknown.

- Short Crohn Disease Activity Index (SCDAI):

This tool has been validated for use in adult crohn's disease patients but is particularly useful for measurement of short-term disease activity and wellbeing. This data will be collected in the crohn's disease patients and includes liquid stools, well-being and abdominal pain²⁵.

- Medication use data:

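### Does using the self-efficacy scale at ages 10-11, below the age of 12 from which it is said to be validated, call for a change to the plan?

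*Combined protocol and SAP*

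**What the plan says.** Section I (Specific Aims) has one item under the secondary aim: "Improves self-efficacy". Section IV, Data collection measures, offers one instrument for it, the General Self-Efficacy Scale, introduced with the words "This is a widely used simple 10 item scale that measures a patient's a general sense of perceived self-efficacy". The entry ends: "It is a measure that has been validated in adolescents age 12 and above". The Inclusion Criteria in the same section admit "Age 10-17 years".

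The closing paragraph of the measures list puts the scale among the repeated assessments, "measure collected at baseline and at the different endpoints (Impact III, peds QL, self efficacy scale, PCDAI, PUCAI", with no age limit. Age itself is recorded at baseline: "Those include age, gender, race, disease type (crohn's, UC), date of diagnosis". Section VI (Benefits and Risks) states an expectation without an age limit: "We anticipate the participants who complete the yoga program will have improved HRQOL and self-efficacy".

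No section restricts the scale to patients of 12 or over, names another instrument for younger children, plans an analysis by age, or explains the scale's use at ages 10 and 11.

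**The concern.** The protocol's own description of the scale leaves out two of the eight eligible years of age, and the scale carries the whole secondary aim. The two quality-of-life questionnaires do not have this problem: their stated ranges (9-17 for IMPACT-III, 8-17 for PedsQL) cover every enrolled age. The short Crohn index is also used outside the population in which it was validated, but its entry says why it was chosen: "validated for use in adult crohn's disease patients but is particularly useful for measurement of short-term disease activity".

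The statistical risk is weaker response to change. If children of 10 and 11 really gain self-efficacy but the scale registers less of that gain, the mean change over all ages is pulled towards zero, and the all-ages result alone would not show it. The within-patient comparison does not remove this kind of error.

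**Working it through.** The plan gives no figure to reproduce here: the power statement under Sample Size concerns the PedsQL total score only, and no power is claimed for self-efficacy. The check asks how much weaker response could matter, and whether an alternative analysis would do better.

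**Inputs**
- n = 34, from Sample Size, taken as complete data.
- m = number aged 10-11. The documents give no age distribution, so m = 3, 8 and 10 are assumptions. An even spread over eight years of age gives 2/8 × 34 = 8.5. Write p = m/34.
- r = share of the older patients' mean change that the scale registers at ages 10-11. This is also assumed: r = 0 as an extreme bound, and r = 0.5.
- Unit: the SD of the within-patient difference between the two changes named under Participants and Enrollment (time 1 to 2, minus time 0 to 1), taken as equal across ages. Section V does not name a paired test; pairing is assumed from the own-control design.
- Yardstick: a change of 0.495 SD at 12 and over, which a two-sided 5% paired t-test on 34 patients detects with 80% power (noncentral t).

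**Formulas**
- Dilution: all-ages mean / 12+ mean = 1 − p + p·r.
- Break-even response, below which the 12+ set has the larger expected test statistic: solve 1 − p + p·r = √(1 − p), so r = (√(1 − p) − (1 − p))/p. For m = 8: (0.8745 − 0.7647)/0.2353 = 0.467.
- Break-even variance ratio (ages 10-11 to 12+) at equal mean change: 1 + 1/(1 − p). For m = 8: 1 + 34/26 = 2.31.
- Expected gap between the 12+ and all-ages estimates: p × 0.495 × (1 − r). Its standard error is √(1/n₁₂ − 1/34), with n₁₂ = 34 − m, because the smaller set lies inside the larger. For m = 8, r = 0: 0.235 × 0.495 = 0.116, and √(1/26 − 1/34) = 0.095.

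| | m = 3 | m = 8 | m = 10 |
|---|---|---|---|
| p | 0.088 | 0.235 | 0.294 |
| Patients aged 12+ | 31 | 26 | 24 |
| Share of the 34 also in the 12+ set | 91% | 76% | 71% |
| Dilution, r = 0 | 0.912 | 0.765 | 0.706 |
| Dilution, r = 0.5 | 0.956 | 0.882 | 0.853 |
| Break-even response r | 0.488 | 0.467 | 0.457 |
| Break-even variance ratio | 2.10 | 2.31 | 2.42 |
| Expected gap, r = 0 (SD) | 0.044 | 0.116 | 0.146 |
| Standard error of gap (SD) | 0.053 | 0.095 | 0.111 |
| Gap / SE, r = 0 | 0.8 | 1.2 | 1.3 |
| Gap / SE, r = 0.5 | 0.4 | 0.6 | 0.7 |

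**Reading**
- At half response, the all-ages mean keeps 85-96% of the older patients' change.
- Dropping ages 10-11 would help only if they registered less than about 46-49% of the change, or had more than 2.10-2.42 times the variance. Nothing in the documents points to either.
- A 12+ estimate set beside the all-ages estimate would usually look consistent with it whether or not the problem exists.

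**The case for a change.** The case for acting is that the protocol sets its own standard. It gives age ranges for both quality-of-life questionnaires and a reason for the short Crohn index, but nothing for self-efficacy at 10-11. One sentence would close the gap at no cost. Naming a 12+ estimate in advance would also prevent an age cut from being chosen after the results are seen, and age is already collected.

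Part of this stands. The mismatch is in the text and is not an artefact of redaction or layout. Weaker response would not cancel in a within-patient comparison.

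The rest carries less weight:
- The contrast with the short Crohn index is thinner than it looks. Its entry explains why it is convenient; it does not show validity in children. The self-efficacy scale gets comparable general support as widely used and simple.
- The Benefits and Risks sentence is an expectation, not an analysis claim about ages 10-11.
- A 12+ estimate fixed in advance would still be too close to the main one to be informative, and agreement between the two could falsely reassure.
- The feared error understates a benefit; it does not create one.

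**Conclusion.** No change to the plan follows. The stated validation starts at 12 and enrolment at 10, with no reason given, but that is a missing line of explanation and not a flaw in the analysis. The entry reports where the scale has been validated; it does not say the scale fails or may not be used below that age. The documents neither show nor exclude weaker response at ages 10-11.

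Analysing all ages is the sensible reading of the plan and, under the assumptions above, the better analysis over most of the plausible range. A rationale or an acknowledged limitation, in the protocol or the eventual report, would be a courtesy to the reader and would change no estimate.

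The dilution and break-even figures rest on an assumed age mix, assumed response shares, equal variances (except for the variance break-even), complete data on 34 patients and a paired analysis. They bound the issue and do not measure it. The point is confined to an unpowered secondary aim.
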